10.1. Exposure

Study drug administration will be listed. For the MAD portion only, the exposure to each dose will be summarized by actual treatment and overall.

10.2. Adverse Events

Adverse events will be coded using the Medical Dictionary for Regulatory Activities (MedDRA) version 21.0 or higher. AEs will be grouped by system organ class (SOC) and preferred term (PT) and summarized by actual treatment. The summary tables will present the number and percentage of total subjects and number of events by SOC and by PT.

All AE summaries will be restricted to treatment emergent AEs (TEAEs) only. Treatment emergent AEs are defined as AEs that commence on or after the time of first study drug administration. Adverse events without an onset date or time or AEs with an onset date of the date of first study drug administration but without an onset time will be defined as treatment emergent, except if an incomplete date (e.g., month and year) clearly indicates that the event started prior to administration of first study drug or if the AE stop date indicates that the event started and stopped prior to administration of first study drug.

Treatment-emergent AEs will be summarized by actual treatment. The number and percentage of subjects experiencing AEs and the number of TEAEs will be tabulated. Subjects who experience the same AE (in terms of MedDRA preferred term) more than once will only be counted once for that event, however, the total number of events will also be counted per category. This also applies to sub-categories displayed in the summaries.

The following summaries will be presented:

- Overall summary of TEAEs
- TEAEs by SOC and PT
- TEAEs by SOC, PT, and severity
- TEAEs by SOC, PT, and relationship to study drug
- Serious TEAEs by SOC and PT

All AEs will be listed. This will include a separate listing of serious adverse events (SAEs), and Non-TEAEs.

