6.2 Exclusion Criteria

1. A history of cardiovascular disease, diabetes or hypertension (Screening assessment >150/90 after 5 minutes sitting), significant neurological, pulmonary (including asthma), hepatic, rheumatic, autoimmune, haematological, metabolic or renal disorder.
2. Prescription medications are prohibited. No prescription medications 2 weeks prior to admission or over-the-counter medications 7 days prior to admission. Occasional use of paracetamol or ibuprofen (up to 1000 mg and 400 mg/day respectively) are acceptable. Routine vitamins and supplements are permissible at the discretion of the investigator
3. Any moderate or severe allergies, including anaphylaxis, to food, drugs or environmental allergens. Mild allergies such as hayfever may be included.
4. Females who are pregnant or lactating. Women of childbearing potential must have a negative pregnancy test within 14 days of study initiation and at baseline.

5. Consumption of caffeine 48 hours prior to start of study treatment and whilst confined to the unit.
6. History of any psychiatric illness or psychological disorder which may impair the ability to provide written informed consent or participate in the study
7. Clinically significant abnormal laboratory value at screening as determined by the Investigator.
8. Participant is sero-positive to HIV-1 or HIV-2, HCV or HBV.
9. History or presence of alcoholism within two years prior to the first study drug administration or drugs of abuse unless it can be explained to the satisfaction of the investigator that it is due to a standard dose of a prescribed medication and that an adequate wash-out will occur prior to admission as per inclusion #5
10. No findings on clinical examination that, in the opinion of the investigator, could compromise the safety of the participant or the results of the study.
11. Blood donation or significant blood loss within 60 days prior to the first study drug administration.
12. Administration of investigational product in another trial within 30 days prior to the first study drug administration or five half-lives, whichever is longer.
13. Surgery within the past 3 months prior to the first study drug administration determined by the PI to be clinically relevant.
14. Active malignancy or history of malignancy in the past 5 years

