- **Day 4.** Participants will undergo a clinical evaluation, including vital signs and a symptom directed physical examination. 25 ml of blood will be drawn for laboratory investigations, including CBC, clinical chemistries, coagulation profile (INR and PTT) and a 72 hour PK sample (from the onset of the first LSALT infusion). A urinalysis, CXR and ECG will also be completed. If the participant shows no adverse events, they will be discharged from the unit.
- **Day 7.** Participants will return for a clinical evaluation, including a brief history, vital signs and a symptom directed physical examination. 25 ml of blood will be drawn for laboratory investigations, including CBC, clinical chemistries, coagulation profile (INR and PTT) and a 96 hour PK sample (from the end of the 3rd LSALT infusion). A urinalysis will also be completed.
- **Day 14.** Participants will return for a clinical evaluation, including a brief history, vital signs and symptom directed physical examination. 25 ml of blood will be drawn for laboratory investigations, including CBC, clinical chemistries. A urinalysis will also be completed and a sample of blood drawn for anti-drug antibodies.
- **Day 21.** Participants will return for a clinical evaluation, including a brief history, vital signs and a complete physical examination. 25 ml of blood will be drawn for laboratory investigations, including CBC, clinical chemistries. A urinalysis and ECG will also be completed. Women of child-bearing age will also have a urine pregnancy test
- **Day 28.** Begin Cohort 2 or 3. Conducted as per Cohort 1 to day 21.

Treatment and Assessment Timetable (MAD)

Study Day	Screen -29 to -2	-1	1	2	3	4	7	14	21
In patient period		X	X	X	X				
Informed consent	X								
Vital signs	X	X	X ⁶	X ⁶	X ⁶	X	X	X	X
Physical Examination	X	X		X	X	X	X	X	X
Alcohol Breath Test	X	X							
Drugs of Abuse	X	X							
Urinalysis	X	X		X		X	X	X	X
CBC	X	X		X		X	X	X	X
Chemistry	X	X		X		X	X	X	X
Creatinine/eGFR	X	X		X		X	X	X	X
LFTs	X	X		X		X	X	X	X
PK			X ¹	X ²	X ³	X ⁴	X ⁵		
INR/PTT	X			X		X	X		
CXR	X					X			
ECG	X	X	X ⁷	X ⁷	X ⁷	X			X

B-hCG ⁸	X	X							X
Adverse Event	X		X	X	X	X	X	X	X
Anti-Drug Antibodies								X	
LSALT Administration			X	X	X				
Discharge from unit						X			
Follow up							X	X	X

Note: Fasting for blood sampling required for Screening and post dose Follow up. Participants will be required to have fasted from all food and drink except water for at least 8 hours prior to blood sampling.

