4.1. Safety Endpoints (Primary)

The primary safety endpoints are:

- Incidence of AEs.
- Clinical laboratory test results (hematology, chemistry, coagulation and urinalysis).
- Vital sign measurements
- 12 lead electrocardiogram (ECG) readings

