		XXXXXXXXXXXX/ YYYYYYYYYYYY/ ZZZZZZZZZZZZ	xxxxxx	DDMONYYYY/ HH:MM/ XX	DDMONYYYY/ HH:MM/ XX	Moderate	Unrelated	Unknown	Unknown

etc.

Adverse Events coded using MedDRA Version X.X.

[1] TEAE = Treatment Emergent Adverse Event.

Listing 16.2.7.3.1 Non-Treatment-Emergent Adverse Events - Low Dose (Intent-to-Treat Population)

Treatment Group: LSALT 0.01 mg

Subject Number	Date/ Time of Study Drug Administration	System Organ Class/ Preferred Term/ Adverse Event	Onset Date/ Time/ Study Day	Resolution Date/ Time/ Study Day	Severity	Outcome	Concomitant Medication Administered
xxxxx	DDMONYYYY/ HH:MM	XXXXXXXXXXXX/ YYYYYYYYYYYY/ ZZZZZZZZZZZZZ	DDMONYYYY/ HH:MM/ XX	DDMONYYYY/ HH:MM/ XX	Mild	Recovering/ Resolving	No
		XXXXXXXXXXXX/ YYYYYYYYYYYY/ ZZZZZZZZZZZZZ	DDMONYYYY/ HH:MM/ XX	DDMONYYYY/ HH:MM/ XX	Moderate	Unknown	Yes

Adverse Events coded using MedDRA Version X.X.

[1] TEAE = Treatment Emergent Adverse Event.

Listing 16.2.7.3.2 Non-Treatment-Emergent Adverse Events - SAD (Intent-to-Treat Population)

Cohort/Treatment Group: Cohort 1/Placebo

Subject Number	Date/ Time of Study Drug Administration	System Organ Class/ Preferred Term/ Adverse Event	Onset Date/ Time/ Study Day	Resolution Date/ Time Study Day	Severity	Outcome	Concomitant Medication Administered
xxxxx	DDMONYYYY/ HH:MM	XXXXXXXXXXXX/ YYYYYYYYYYYY/ ZZZZZZZZZZZZZ	DDMONYYYY/ HH:MM/ XX	DDMONYYYY/ HH:MM/ XX	Mild	Recovering/ Resolving	No
		XXXXXXXXXXXX/ YYYYYYYYYYYY/ ZZZZZZZZZZZZZ	DDMONYYYY/ HH:MM/ XX	DDMONYYYY/ HH:MM/ XX	Moderate	Unknown	Yes

Adverse Events coded using MedDRA Version X.X.

[1] TEAE = Treatment Emergent Adverse Event.

Listing 16.2.7.3.3 Non-Treatment-Emergent Adverse Events - MAD (Intent-to-Treat Population)

Cohort/Treatment Group: Cohort 4/Placebo

Subject Number	Date/ Time of Study Drug Administration	System Organ Class/ Preferred Term/ Adverse Event	Onset Date/ Time/ Study Day	Resolution Date/ Time/ Study Day	Severity	Outcome	Concomitant Medication Administered
xxxxx	DDMONYYYY/ HH:MM	XXXXXXXXXXXX/ YYYYYYYYYYYY/ ZZZZZZZZZZZZZ	DDMONYYYY/ HH:MM/ XX	DDMONYYYY/ HH:MM/ XX	Mild	Recovering/ Resolving	No
		XXXXXXXXXXXX/ YYYYYYYYYYYY/ ZZZZZZZZZZZZZ	DDMONYYYY/ HH:MM/ XX	DDMONYYYY/ HH:MM/ XX	Moderate	Unknown	Yes

Adverse Events coded using MedDRA Version X.X.

[1] TEAE = Treatment Emergent Adverse Event.

Listing 16.2.8.1.1.1 Hematology - Low Dose (Intent-to-Treat Population)

Treatment Group: LSALT 0.01 mg

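### The SAP's onset-only definition of a treatment-emergent event leaves a pre-dose event that worsens after dosing out of every AE summary, in either arm, unless the site opens a new AE record

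*SAP*

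**What the plan says.** SAP 4.1 names four primary safety endpoints, and the first is "Incidence of AEs". SAP 10.2 sets the rule for summarizing it: "Treatment emergent AEs are defined as AEs that commence on or after the time of first study drug administration". It adds: "All AE summaries will be restricted to treatment emergent AEs (TEAEs) only".

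The definition has one extension, which begins "Adverse events without an onset date or time or AEs with an onset date of the date of first study drug administration". It counts events with a missing onset date or time, or a dosing-day onset without a time, as treatment-emergent unless the available dates place them before dosing. It says nothing about severity.

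Five summaries follow: overall, by SOC and PT, by severity, by relationship, and serious events. For everything else the SAP relies on listings: "All AEs will be listed. This will include a separate listing of serious adverse events (SAEs), and Non-TEAEs".

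Protocol 16.0 also ties treatment-emergent events to the period after dosing and has no worsening clause. Protocol 9.1 and 9.2 define and grade AEs but do not say how a change of grade in an existing event is to be recorded.

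**The concern.** Pre-dose events should be expected in this database. The AE row of the assessment timetables is marked at screening, and the SAP provides shells for listing non-treatment-emergent events. The design also makes mild pre-dose complaints plausible. One exclusion criterion reads "Consumption of caffeine 48 hours prior to start of study treatment and whilst confined to the unit", light smokers must abstain while confined, mild hay fever is allowed, and blood is drawn on Day -1.

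Take a participant with a Grade 1 headache on Day -1 that becomes Grade 2 or 3 during the infusion. Read literally, SAP 10.2 classes it by its Day -1 onset, and the later course does not change that.

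The other primary endpoints are handled differently. Laboratory values, vital signs and ECG get change from baseline and shift tables (SAP 10.3 to 10.5), so deterioration from the pre-dose state is summarized for them. For AEs it is not. The safety analysis is descriptive and has no planned test, so the summary tables carry much of the reported conclusion. An event that helped to pause the study could be missing from the severity and relationship tables.

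**Working it through.** The plan gives no figure to reproduce: SAP 3.5 states that power was not calculated. The check is a trace through the text, followed by simple proportions.

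**Step 1. Follow one event.** Onset before the first dose at Grade 1, rising to Grade 3 afterwards.

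| Where | Worsening entered as a grade change on the same record | Worsening entered as a new AE |
|---|---|---|
| Five TEAE summaries (SAP 10.2) | Absent (from the serious summary too, if it becomes serious) | New record counted |
| All-AE listings (16.2.7.1.x) | Present, with seriousness, severity, relationship, action taken and TEAE flag | Both records present |
| SAE listings (16.2.7.2.x), if serious | Present | Present |
| Non-TEAE listings (16.2.7.3.x) | Present, but without columns for seriousness, relationship or action taken | Pre-dose record only |
| Pause rule (Protocol 8.0) and unblinding (Protocol 9.9) | Counts, because both work by grade | Counts |

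**Step 2. Is the second column required?** No. Nothing in Protocol 9.1, 9.2 or 16.0, or in SAP 10.2, tells the site to open a new AE on worsening. The SAP cites eCRF version 4.00, but its completion instructions are not among the documents, so actual practice is unknown.

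**Step 3. Size for one participant.** Inputs: 6 active and 2 placebo per cohort (SAP 3.3 and 3.6); placebo pooled, with each study part presented separately (SAP 6.1).

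- Active dose group: n = 6. Pooled placebo per part: 3 cohorts × 2 = 6.
- If the participant has no other TEAE, the table shows 0/6 = 0% under the current rule and 1/6 = 16.7% with a worsening clause. The difference is 16.7 percentage points in either kind of column.
- Clopper-Pearson 95% intervals: 0/6 gives 0 to 45.9%; 1/6 gives 0.4 to 64.1%.
- If the participant has another TEAE, the any-TEAE row does not move, though the SOC/PT, severity or relationship rows may.

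**Step 4. How often.** The documents give no rate, so q, the chance that a participant has such an event, is an assumption. The probability that at least one of 6 is affected is 1 − (1 − q)^6:

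| Assumed q | Calculation | Result |
|---|---|---|
| 2% | 1 − 0.98^6 | 11.4% |
| 5% | 1 − 0.95^6 | 26.5% |
| 10% | 1 − 0.90^6 | 46.9% |

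**The case against.** The strongest reply is that nothing is lost from the report. Every AE is listed, and the all-AE listing carries seriousness, relationship and action taken. With 8 participants per cohort the listings can be read in full. Participant protection does not depend on TEAE status. The participants are screened healthy volunteers, so such events should be few. The intervals for 0/6 and 1/6 overlap almost entirely. If the site already opens a new AE on worsening, the loss is nil. All of this stands and limits the weight of the point. It does not supply the missing clause: the tables that summarize a primary endpoint can still omit the event when the written rule is followed.

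Two stronger readings are tempting, and the documents support neither.

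- A reader might infer that the rule biases the comparison toward no drug effect. It takes no account of treatment and removes worsening on placebo and natural-course worsening in the same way. Caffeine withdrawal, smoking abstinence and hay fever would occur in both arms. The displayed incidence can only fall, but no direction between arms is shown.
- A reader might infer that the MAD timetable makes matters worse, because its AE row is blank on Day -1 while the SAD row is marked. For an event first elicited on Day 1 with no recorded onset time, SAP 10.2 leans the other way: the event counts as treatment-emergent unless the dates show a pre-dose start.

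A practical objection also stands. The AE listing shells show one severity field per event. If the eCRF matches them, a change of definition alone could not separate the pre-dose grade from the post-dose grade.

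**Conclusion.** The gap is real and should be closed. As written, a pre-dose event that worsens after dosing is left out of all five AE summaries, in whichever arm it occurs. It remains in the listings and still counts toward the pause rule.

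For one affected participant, the displayed incidence in a group of 6 is 0/6 instead of 1/6, a difference of 16.7 percentage points. This rests on two conditions: the site records the worsening on the existing AE, and the participant has no other TEAE. The absence of the clause is certain from the text. How often it would matter is not, since the documents give no rate of pre-dose events and no eCRF instructions. The finding concerns the completeness of the summaries. It does not show a bias between arms or a failure of safety oversight.

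**What to change.** In SAP 10.2, define a TEAE as an AE that begins at or after the first dose of study drug, or one that was present earlier and later increases in severity or becomes serious. Apply the same definition to the Serious TEAE tables and the Non-TEAE listing.

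To make this workable with one severity field per event, add a recording rule: worsening after dosing is entered as a new AE record with its own onset date, time and grade. The pre-dose record then stays in the Non-TEAE listing at its own grade, and the new record enters the summaries.

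The cost is a sentence in the SAP, a recording instruction for the site and a small programming change. Protocol 3.7 reports six cohorts already completed. For those, the recording rule comes too late, and AEs with a pre-dose onset would have to be checked by data query before database lock. The downside is that a few more events may appear in the TEAE tables, including natural-course worsening in either arm.

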10.3. Laboratory Evaluations

Laboratory data (hematology, chemistry and coagulation) will be summarized at each protocol-scheduled visit, by actual treatment. Actual values and actual changes from baseline will be presented.

In addition, a shift table representing the categorical change in laboratory results interpretation (normal, abnormal not clinically significant, or abnormal clinically significant) from baseline to each post baseline visit will be presented.

This document is confidential.

Urinalysis results evaluation will be summarized at each protocol-scheduled timepoint, by actual treatment, using frequency tabulations.

High and low/abnormal results will be flagged in the listings.

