3.4 Pre-Clinical Data for Dipeptidase-I and LSALT Peptide in Acute Kidney Injury

1.4.1. DPEP-1 expression and function in kidney, liver, and lung. DPEP-1 expression and localization was characterized in renal tubular epithelial cells (TEC) cultured from human nephrectomy tissue samples were labeled with either zonula occludens-1 (ZO-1), a tight junction protein found on TEC, and DPEP-1. Confocal microscopy confirmed the expression of DPEP-1 on the surface of TEC. Additional characterization of DPEP-1 using immunohistochemical analysis revealed high expression levels in mouse kidney epithelium and endothelium as well as expression in lung and liver endothelium. Similar expression patterns have been confirmed in human lung, liver and kidney. Using immunoblotting, DPEP-1 expression was found in both total kidney lysates and isolated TEC which confirmed the microscopy findings. Although DPEP-1 is predicted to have a size of 42kDa, a 55kDa DPEP-1 protein was also detected due to the presence of a GPI anchor as well as post-translational glycosylation as demonstrated by the effects of PNGaseF. Functional activity of DPEP-1 was determined in various samples using fluorescent enzyme activity assay that demonstrated high levels of dipeptidase activity in both human and mouse kidney tissue.

1.4.2. Specificity of LSALT Peptide binding to DPEP-1. DPEP-1 as a binding target for LSALT peptide was confirmed by overexpressing rat, canine or human DPEP-1 in Cos-1 cells and treated with fluorescently labeled LSALT peptide. Analysis with fluorescent confocal microscopy of these cells demonstrated that LSALT peptide was bound only to cells expressing DPEP-1. This specific interaction was confirmed using a biotin-labeled LSALT peptide immunoprecipitation assay of DPEP-1. Total protein lysates from DPEP-1 overexpressing cells were treated with biotin-labeled LSALT peptide and the protein complex was pulled down with neutravidin conjugated beads before analysis by

immunoblotting using anti-DPEP-1 antibody. Immunoblot analysis revealed that DPEP-1 interacted with LSALT peptide but not non-specific control peptide indicating specificity of LSALT peptide binding to DPEP-1.

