[1] Baseline is defined as the last available, non-missing assessment on or prior to first study drug administration.

NCS = Not Clinically Significant, CS = Clinically Significant.

Programming Note: Continue for all protocol scheduled visits/time points and all chemistry parameters.

Table 14.3.4.1.6.3 Coagulation Shifts From Baseline - MAD (Safety Population)

Treatment Group: All Placebo (N=xxxx)

Parameter (unit)	Visit	Baseline[1]	Post Baseline[1]			
			Normal	Abnormal NCS	Abnormal CS	Missing
INR (unit)	Day XX	Normal	xx (xx.x%)	xx (xx.x%)	xx (xx.x%)	xx (xx.x%)
		Abnormal NCS	xx (xx.x%)	xx (xx.x%)	xx (xx.x%)	xx (xx.x%)
		Abnormal CS	xx (xx.x%)	xx (xx.x%)	xx (xx.x%)	xx (xx.x%)
		Missing	xx (xx.x%)	xx (xx.x%)	xx (xx.x%)	xx (xx.x%)
	Day XX	Normal	xx (xx.x%)	xx (xx.x%)	xx (xx.x%)	xx (xx.x%)
		Abnormal NCS	xx (xx.x%)	xx (xx.x%)	xx (xx.x%)	xx (xx.x%)
		Abnormal CS	xx (xx.x%)	xx (xx.x%)	xx (xx.x%)	xx (xx.x%)
		Missing	xx (xx.x%)	xx (xx.x%)	xx (xx.x%)	xx (xx.x%)

etc.

[1] Baseline is defined as the last available, non-missing assessment on or prior to first study drug administration.

NCS = Not Clinically Significant, CS = Clinically Significant.

Programming Note: Continue for all protocol scheduled visits/time points and all chemistry parameters.

Table 14.3.4.1.7.2 Urinalysis Results Evaluation - SAD (Safety Population)

Parameter (unit)	Visit	Result	All Placebo (N=xxx)	etc. (N=xxx)
Glucose (mmol/L)	Baseline[1]	Positive	xx (xx.x%)	xx (xx.x%)
		Negative	xx (xx.x%)	xx (xx.x%)
	Day XX	Positive	xx (xx.x%)	xx (xx.x%)
		Negative	xx (xx.x%)	xx (xx.x%)
etc.				

[1] Baseline is defined as the last available, non-missing assessment prior to first study drug administration.

Programming Note: Continue for all protocol scheduled visits and all urinalysis parameters.

Table 14.3.4.1.7.3 Urinalysis Results Evaluation - MAD (Safety Population)

Parameter (unit)	Visit	Result	All Placebo (N=xxx)	etc. (N=xxx)
Glucose (mmol/L)	Baseline[1]	Positive	xx (xx.x%)	xx (xx.x%)
		Negative	xx (xx.x%)	xx (xx.x%)
	Day XX	Positive	xx (xx.x%)	xx (xx.x%)
		Negative	xx (xx.x%)	xx (xx.x%)
etc.				

[1] Baseline is defined as the last available, non-missing assessment prior to first study drug administration.

Programming Note: Continue for all protocol scheduled visits and all urinalysis parameters.

Table 14.3.4.2.1.2 Vital Signs - SAD (Safety Population)

Parameter (unit)	Visit	All Placebo (N=xxx)	etc. (N=xxx)
Scheduled Timepoint			
Pulse Rate (beats/min)			
Baseline[1]			

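### Urinalysis, part of the primary safety endpoint, is summarised only as Positive/Negative counts per visit; a baseline shift table would show new positives per dose group directly

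*SAP*

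**What the plan says.** SAP 4.1 lists among the primary safety endpoints "Clinical laboratory test results (hematology, chemistry, coagulation and urinalysis".

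SAP 10.3 then treats the panels differently. For three of them it says "Laboratory data (hematology, chemistry and coagulation) will be summarized at each protocol-scheduled visit, by actual treatment", with actual values and changes from baseline, and it continues "In addition, a shift table representing the categorical change in laboratory results interpretation", from baseline to each later visit. Urinalysis has its own sentence after that: "Urinalysis results evaluation will be summarized at each protocol-scheduled timepoint, by actual treatment, using frequency tabulations". The section ends by asking for abnormal results to be flagged in the listings.

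The shells in SAP Section 16 agree with the text. Hematology, chemistry and coagulation each have a shift table for SAD and for MAD. Urinalysis has only Tables 14.3.4.1.7.2 and 14.3.4.1.7.3, with a Positive row and a Negative row at baseline and again at each later day. The table does define its baseline: "Baseline is defined as the last available, non-missing assessment prior to first study drug administration". Vital signs and ECG, the other measured primary endpoints, get shift tables under SAP 10.4 and 10.5.

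**The concern.** Counts at baseline beside counts at a later visit are the two margins of a paired table. They do not show who changed. Equal counts before and after dosing can mean that nobody changed, or that some participants became positive while others became negative. A shift table keeps the pairing, and the SAP already uses one for every other measured safety endpoint.

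The summary matters somewhat more here than in many phase I studies. Protocol 3.8 gives prevention of acute kidney injury as the purpose of development, and Protocol 3.4 says of the drug's target that "immunohistochemical analysis revealed high expression levels in mouse kidney epithelium and endothelium". A reader of the final report will probably want to know, per dose, how many participants negative for urinary protein or blood before dosing were positive afterwards. The planned table does not in general give that number.

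**Working it through.** The plan states no figure for this point, so there is none to reproduce. The check has four steps.

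**1. Can baseline positives occur?** Yes. Inclusion criterion 3 (Protocol 6.1) asks for normal urinalysis at screening but admits abnormalities the investigator judges not clinically significant. Exclusion criterion 7 (Protocol 6.2) bars only clinically significant ones. The documents give no rate of baseline positives.

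**2. What do the margins determine?** Each dose group has 6 active participants (SAP 3.6). Placebo is pooled within a study part (SAP 6.1), which gives 3 cohorts × 2 = 6. Every column therefore has n = 6. With a positive at baseline and b positive at a later visit, and no missing results:

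- fewest new positives = max(0, b − a)
- most new positives = min(b, 6 − a)

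| Positive at baseline (a) | Positive later (b) | New positives |
|---|---|---|
| 0 | 2 | 2 (exact) |
| 1 | 1 | 0 to 1 |
| 2 | 2 | 0 to 2 |
| 3 | 3 | 0 to 3 |

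The counts a and b are assumed for illustration. For a = b = 2, the range 0 to 2 is 0% to 50% of the 6 − 2 = 4 participants negative at baseline.

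The width of the range is min(a, b, 6 − a, 6 − b). It is zero whenever a or b is 0 or 6, and positive when both lie between 1 and 5. That is 5 × 5 = 25 of the 7 × 7 = 49 possible pairs. This counts patterns and is not a probability: if nobody is positive at baseline, the planned table already gives the exact answer.

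**3. Can the number be recovered elsewhere?** Yes. Listings 16.2.8.1.4.1 to 16.2.8.1.4.3 show each participant's result by parameter at screening, at Day -1 (marked as baseline) and at each later visit. The work is clerical. The Protocol timetables schedule post-dose urinalysis on Days 2 and 7 in SAD and on Days 2, 4, 7, 14 and 21 in MAD. For five categorical analytes and 24 participants per part, the comparisons are 5 × 24 × 2 = 240 in SAD and 5 × 24 × 5 = 600 in MAD, 840 in all. The listings are sorted by cohort and randomised treatment (SAP 6.1), so placebo participants are spread over three cohorts, while the summaries use actual treatment.

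**4. Does the layout suit every parameter?** Not pH. Protocol 7.3.6 includes pH in the dipstick. The table shell shows glucose as Positive/Negative and tells the programmer to continue for all urinalysis parameters. The listing shell does allow numeric urinalysis values with a normal range.

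**The case against.** The strongest objection is that nothing is lost. The listings report the pairing in full, with abnormal flags, and with 6 participants per column it can be checked by eye. Eligibility makes baseline positives uncommon, and with none the planned table is exact. Numeric change from baseline has no meaning for a positive/negative result. Kidney safety has other cover: creatinine and urea are in the chemistry panel, which gets changes and shift tables, and a urinary abnormality recorded as an adverse event would appear in the treatment-emergent tables of SAP 10.2. No escalation or stopping rule in Protocol 8.0 refers to this table.

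Most of this stands, and it limits the point. A reader might infer that new positives cannot be told from existing ones at all; the listings show otherwise. A reader might take the missing change from baseline as a fault; for dichotomous results it is not. A reader might infer that renal harm would go unseen; the chemistry and adverse event summaries do not support that, and the expression data describe where the target is found (lung and liver as well as kidney), not toxicity. Nor do the shells settle that pH would be forced into Positive/Negative, since one sample parameter is shown.

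The objection does not explain why urinalysis should be the exception. Listings exist for the other panels too, and the SAP still plans shift tables for them. Baseline positives may be few, but they are permitted.

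**Conclusion.** The point holds as a modest improvement. Urinalysis is the only measured component of the primary safety endpoints without a baseline shift table, so from the summary tables its new positives per group are in general only bounded. The size depends on how many participants are positive at baseline, which the documents do not give: no uncertainty if none is, and up to 3 participants wide in a group of 6 if half are positive at both visits. The bounds assume complete results. Sample size, error rates and trial conduct are unaffected, and no conclusion is out of reach for someone who works through the listings.

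**What to change.** In SAP 10.3 and the shells for Tables 14.3.4.1.7.2 and 14.3.4.1.7.3, present protein, blood, glucose, ketones and leukocytes as a shift table from baseline to each scheduled post-baseline visit, by actual treatment. Use negative, positive and missing as categories, or the recorded dipstick categories if these are captured. The grid of the hematology shift shell can be reused with these categories. Its row and column totals reproduce the counts now planned, so nothing is given up. State that pH is summarised as a numeric variable and not in the Positive/Negative layout. A worst post-baseline row is not needed for parity, as no other laboratory panel has one.

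The cost is a change of SAP wording and one re-formatted table per study part. No new data are needed.
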